### **3.4.2 Assessment of Musculoskeletal MRI Muscle Fat Fraction, Lean Muscle Volume and Muscle Fat Infiltration**

Measurement of the extent of skeletal muscle tissue replacement by fat in FSHD patients will be done through automatic skeletal muscle segmentation for the 3D muscle volumes and fat fraction analysis via robust algorithms using Dixon imaging. This will be assessed at Screening and Week 36.

#### **Composite measures:**

Composite variables, incorporating pre-selected muscles, will be derived for longitudinal analysis of muscle fat fraction, lean muscle volume and muscle fat infiltration (MFFtot, LMVtot, and MFItot respectively). The longitudinal composite observations of relative change in LMV are sensitive to low overall LMV, therefore an exclusion criterium is applied for such observations. See [Appendix 6](#) for derivations and exclusion criteria. The scores will be derived and exclusions applied by scientists at the MRI Service Provider (AMRA Medical Inc.).

Descriptive statistics of MFFtot, LMVtot, and MFItot per visit as well as changes from baseline will be presented for the whole body, as well as muscle regions as applicable. Missing visit observations will be back calculated from provided screening and change from screening values.

#### **Individual Muscles:**

For each muscle location, a similar method will be used to analyze muscle fat fraction (%), lean muscle volume (cL), and muscle fat infiltration (%) per visit as well as changes from baseline.

#### **Correlation:**

Spearman correlations between MRI composite measures of classic TUG, FSHD TUG, and RWS and traditional measures of classic TUG, FSHD TUG, and RWS will be calculated. Correlations and p-values will be presented by visit. RWS correlations will be presented by dominant and non-dominant hand.

### **3.4.3 Skeletal Muscle Echogenicity by Ultrasound**

Ultrasound for skeletal muscle will be measured at Baseline (Day 1), Week 14, Week 24, Week 36, and End of Treatment (Week 60). Ultrasound analysis will be performed by an outside vendor.

### **3.4.4 Reachable Work Space With and Without Weights**

The reachable work space (RWS) is a 3-dimensional sensor-based system (using a single depth-ranging sensor) that can unobtrusively detect an individual's RWS and reflects an individual global upper extremity function, including shoulder and proximal arm. The evaluation will be performed with and without weights and on both the right and left arms at Baseline (Day 1), Week 4, Week 8, Week 14, Week 24, Week 36, Week 48, and End of Treatment (Week 60).

The absolute total RWS surface envelope area (m^2) as well as areas for each of the quadrants will be calculated and provided by a vendor in a blinded fashion. The reachable workspace relative surface area (RSA) represents the portion of the unit hemisphere that is covered by an individual's hand movement.

Descriptive statistics of RSA results per visit as well as the change from baseline will be presented by quadrant, for total upper quadrants (Q1+Q3), total area (Q1+Q2+Q3+Q4), and total area (Q1+Q2+Q3+Q4+Q5) for the assessment with weights and without weights, and by dominant and non-dominant arm. Summary tables will be generated, showing percentage of subjects with RSA decline of  $\geq 5\%$ ,  $\geq 2\%$  at each post-baseline timepoint. The functional work space (FWS) will also be summarized using number and percentages of subjects belonging to the categories of normal or low speed. The detected time within each target will be presented in a listing.

### **3.4.5 Classic and FSHD TUG**

The TUG test is used to assess a person's mobility and requires both static and dynamic balance. It measures the time that a person takes to rise from a chair, walk 3 meters, turn around, walk back to the chair, and sit down. The FSHD TUG test is the classic TUG but adds the component of getting up from a laying position on a bed-like table in the clinic at the start of the test and laying back down on his or her back at the end of the test. The FSHD TUG will capture total completion time and completion times for each segment (supine to sit, stand-walk-sit, and sit to supine). Each test will be done twice per visit and will be assessed at Screening, Week 4, Week 8, Week 14, Week 24, Week 36, Week 48, and End of Treatment (Week 60).

The average of Trial 1 and Trial 2 assessments at each visit will be derived for both the classic TUG completion time and each of the FSHD TUG completion times (ie, supine to sit, stand-walk-sit, sit to supine, and total) will be used for the analysis.

Descriptive statistics of classic TUG average completion time and FSHD TUG average completion times in seconds per visit as well as the change from baseline will be provided in tables. The average completion time of the FSHD TUG is a key study endpoint. Descriptive statistics of FSHD TUG average completion times will be presented for each segment (supine to sit, stand-walk-sit, sit to supine, and total). Similar analysis will also be conducted for each of the individual components of the FSHD TUG.

### **3.4.6 FSHD-HI**

The FSHD-HI is an FSHD-specific patient-reported measure of disease burden on activities of daily living, quality of life, and symptom prevalence and severity. It consists of a questionnaire with 116 items developed from qualitative interviews of patients. The measure consists of 14 subscales that measure a patient's perception of their ambulation and mobility, hand function, shoulder and arm function, emotional health, back/chest/abdomen strength, fatigue, pain, eating function, ability to do activities,

communication ability, satisfaction in social situations, performance situations, body image and cognition. The 116 items are combined into a total score, the score is then transformed onto a percentage scale, with 100 representing maximal disability and lower scores representing decreasing disability. This FSHD-HI total score will be calculated by a separate vendor. This score, along with the 14 subscale scores will be assessed at Screening, Week 4, Week 24, and End of Treatment (Week 60).

Descriptive of the FSHD-HI total and subscale scores per visit as well as the change from baseline will be presented.

#### **3.4.7 FSHD-RODS**

The FSHD-RODS is a patient-reported, linearly weighted scale that precisely measures activities of daily living and participation in subjects with FSHD using 50 items based on the Rasch model. This will be assessed at Screening, Week 4, Week 24, and End of Treatment (Week 60).

Descriptive statistics of the FSHD-RODS total and subscale scores per visit as well as the change from baseline will be presented.

#### **3.4.8 Dynamometry**

Dynamometry measures the static muscle strength without any movement. Manual dynamometry with hand-held devices and quantitative myometry testing (QMT) with bedframe equipment will be used to assess the skeletal muscle strength of study subjects in both the upper and lower limbs bilaterally. Manual dynamometry be assessed at Screening, Week 4, Week 14, Week 24, Week 48, and End of Treatment (Week 60). QMT will be assessed at Screening, Week 4, and End of Treatment (Week 60).

Descriptive statistics for percent predicted QMT as well as change from baseline will be presented for: (a.) all muscles combined; (b.) upper extremity strength, which includes the hands, shoulders and elbows combined; and (c.) lower extremity strength, which includes knee extension, knee flexion, and ankle dorsiflexors combined. Percent predicted QMT scores will be calculated using SAS® code provided in [Appendix 9](#) (with additional extremity details in [Appendix 10](#)).

Descriptive statistics for total manual dynamometry as well as change from baseline will be presented for: (a.) all muscles combined; (b.) upper extremity strength, which includes the hands, shoulders and elbows combined; and (c.) lower extremity strength, which includes right and left ankle dorsiflexors combined. Raw scores will be presented.

Descriptive statistics of manual dynamometry average and maximum weight in kilogram per visit as well as the change from baseline and percent change from baseline will be presented according to assessment (dominant shoulder abductors, non-dominant shoulder abductors, dominant elbow flexors, non-dominant elbow flexors, dominant elbow

extensors, non-dominant elbow extensors, dominant hand grip, non-dominant hand grip, right ankle dorsiflexors, and left ankle dorsiflexors). Raw scores will be presented.

Descriptive statistics of normalized manual dynamometry average and maximum weight in kilogram per visit as well as the change from baseline will be presented by overall upper extremity and according to assessment (dominant shoulder abductors, non-dominant shoulder abductors, dominant elbow flexors, non-dominant elbow flexors, dominant elbow extensors, non-dominant elbow extensors, dominant hand grip, and non-dominant hand grip).

Manual dynamometry data will be normalized as (subject measure – reference mean)/reference standard deviation. For elbow flexion, elbow extension, and shoulder abduction the reference mean and standard deviation (converted to kg from Newton) from Douma et al. (see Appendix 7) will be used. For hand grip the reference mean and standard deviation from the Jamar® Smart Hand Dynamometer (see Appendix 8) will be used.

### **3.4.9 MMT**

Manual muscle testing is one of the most commonly used forms of muscle testing. Subjects hold the corresponding limb or appropriate body part to be tested at the end of its available range while the evaluator provided opposing manual resistance.

Descriptive statistics for MMT as well as change from first observation will be presented for: (a.) all muscles combined; (b.) upper extremity strength; (c.) lower extremity strength; and (d.) individual muscles. See [Appendix 11](#) for MMT raw score mapping.

### **3.4.10 PGIC**

The PGIC is self-reported and reflects a subject's belief about efficacy of treatment. PGIC is a 7-point scale depicting a subject's rating of overall improvement. This will be assessed at Week 14, Week 24, Week 36, Week 48, and End of Treatment (Week 60).

Descriptive statistics of the PGIC responses per visit will be presented.

### **3.4.11 Outpatient Mobility Assessment**

Upper and lower limb mobility in the outpatient setting using wearables will be measured at Baseline (visit 2) and intermittently to end of study. Mobility assessment will be analyzed by an outside vendor.

### **3.4.12 MFM Domain 1**

The MFM scale measures the severity of the motor deficit in the main neuromuscular diseases as determined by a physical therapist. The total score provides a good measure of the overall functional severity across various domains. Domain 1 is used in this trial and focuses on ambulation and transfers ability. This will be assessed at Screening, Week 8, Week 24, Week 48, and End of Treatment (Week 60).

Descriptive statistics of scores per visit as well as the change from baseline will be presented by overall and according to assessment (lift pelvis in supine, lying to sitting, long sitting to standing up, sitting down on a chair, standing up from a chair, stand, standing on one foot, touching the floor while standing, walk on heels, walk on line, run, hop, squat).

### **3.4.13 Spirometry**

Spirometry will be measured to assess the change from the pre-treatment period in lung ventilatory function. Forced vital capacity (FVC) and forced expiratory volume in 1 second (FEV1) will be assessed at Baseline (visit 2), Week 24, Week 48, and End of Treatment (Week 60).

Descriptive statistics of FVC and FEV1 per visit as well as the change from baseline will be presented.

### **3.4.14 6-MWT**

The 6-MWT will be performed to evaluate the change from the pre-treatment period in the distance a subject is able to walk over a total of 6 minutes. A course length of 20 meters will be marked with 2 traffic cones and subjects will be instructed to walk back and forth around the cones for 6 minutes. The distance walked during the first 2 minutes and the full 6 minutes will be recorded. This will be assessed at Screening, Week 4, Week 8, Week 14, Week 24, Week 36, Week 48, and End of Treatment (Week 60).

Descriptive statistics of the total distance walked per visit as well as the change from baseline will be presented.

## **3.5 OTHER EXPLORATORY ANALYSIS**

Other exploratory analyses may be conducted as appropriate. Any exploratory analyses that are performed will be appropriately titled/labeled as ‘exploratory’ and will be clearly distinguished from planned analyses when results are reported in the Clinical Study Report (CSR).

Graphic methods - like box plots and spaghetti plots - may also be used to describe exploratory endpoints.

Descriptive statistics of Ricci scores per visit as well as the change from baseline will be presented.

## **3.6 SENSITIVITY ANALYSIS**

Sensitivity analyses will be conducted using an alternative baseline defined as the mean of all available pre-treatment measures. Selected exploratory endpoints will be repeated using the alternative baseline definition.

The sensitivity endpoints are as follows:

- Reachable Work Space (RWS) with and without weights
- Disease impact by subject report using FSHD-Rasch-built Overall Disability Scale (FSHD-RODS)
- Disease impact by subject report using FSHD-HI
- Physical function by Motor Function Measure (MFM) domain 1
- Manual Dynamometry
- Classic TUG and FSHD TUG
- Change in ambulation as measured by the 6-minute walking test (6-MWT)

## 4 INTERIM ANALYSIS

### 4.1 INTERIM ANALYSIS (IA)

There are two formal IAs planned:

- the first analysis will occur after approximately 6-8 subjects have completed the visit 5 biopsy (Week 4 or Week 8, post-treatment visit). For some subjects, the visit 5 biopsy occurs at 4-weeks post-treatment, and for others, it occurs at 8-weeks post-treatment. Analysis of DUX4 will be provided at baseline, Week 4 post-treatment and Week 8 post-treatment, with the corresponding change measures.
- the second IA will occur after approximately 6-8 subjects have completed Visit 7 (Week 36).

Further details of data to be analyzed and presented for each IA are described below:

#### IA #1 (n = 6 to 8 subjects):

- Summary table of Baseline demographics and disease characteristics (including baseline Ricci Scores)
- Medical History Summary
- PK/PD Summaries
- Summary tables of DUX4 activity for each of 11 gene transcripts: CCNA1; KHDC1L; LEUTX; MBD3L2; PRAMEF6; PRAMEF9; SLC2A3; SLC34A2; TRIM43; ZSCAN4; DUX4fl
  - Baseline, Week 4 post-baseline, Week 8 post-baseline and Change from Baseline summaries by gene transcript
- Summary tables expression levels for each of 18 transcripts: PNP; RBP7; MYH3; ACTA2; TNNT2; COMP; POSTN; SAA1; CCL13; FST; PLA2G2A; S100A6; C3; ADIPOQ; LEP; COL1A1; THBS4; TAGLN2
  - Baseline, Week 4 post-baseline, Week 8 post-baseline and Change from Baseline summaries by gene transcript
- Summary tables of DUX4 disease activity based on:
  - DUX4 Composite Score: Based on 6 gene transcripts. See Section 3.4 and Appendices 1-5.

---

- Box plots of DUX4 summary data, over time.

#### **IA #2 (n = minimum 6 to 8 subjects and up to 14 subjects)**

- Summary table of Baseline demographics and disease characteristics.
- Summary tables of MRI parameters, by different muscle location and whole body. MRI parameters include: Musculoskeletal MRI Fat Fraction; Musculoskeletal MRI Fat Infiltration; Musculoskeletal MRI Lean Muscle Volume; and composite scores of MRI measurements for whole body and regions (see [Appendix 6](#)).
  - Baseline, Visit 7/Visit 8 and Change from Baseline summaries by MRI parameter and location.
- Summary tables of classic TUG and FSHD TUG.
- PK Summaries
- Summary table of muscle strength by quantitative dynamometry
- Summary table of muscle strength by hand-held dynamometry
- Summary table of distance of walking measured by 6-MWT
- Summary table of reachable work space (RWS)
- Summary table lung function as measured by Spirometry
- Summary table of physical function by MFM domain 1
- Summary table of FSHD-HI total score
- Summary table patient global impression of change
- Summary table of FSHD-RODS total score

#### **4.2 DATA MONITORING COMMITTEE**

NA

### **5 SUMMARY OF MAJOR CHANGES IN THE PLANNED ANALYSES**

Due to missed visits related to COVID-19, the FSHD-RODS and FSHD-HI results are presented by protocol visit as opposed to analysis weeks. Visits 6 and 7 are combined as individual subject visits were split between these two visits.

Due to missed visits related to COVID-19, the MRI results are presented by protocol visit as opposed to analysis weeks. Visits 7 and 8 are combined as individual subject visits were split between these two visits.

## 7 APPENDICES

### APPENDIX 1: THE STEPS FROM RAW QPCR CT TO STATISTICAL ANALYSIS

1. Raw Cts from qPCR are determined for DUX4 regulated genes using a validated assay (Fluidigm), described in Appendix 2.
2. The raw Cts from the genes are normalized to reference (housekeeping) genes using the process described in Appendix 3. The document also describes the method for selecting the reference genes.
3. A composite DUX4 score is created for each subject using the normalized data, at baseline and post-baseline, using the derivation described in Appendix 4.
  - a. Six DUX4-regulated gene transcripts were selected, a priori, to be in a composite DUX4 score. The process of selection of these 6 genes is detailed in Appendix 5.
4. Summary data is generated for the DUX4 composite score at baseline and post-baseline, to assess “change” over time.

[figure not shown]

#### APPENDIX 4: DERIVATION OF COMPOSITE DUX4 SCORE FROM DELTA CT

**Select only rows pertaining to the following 6 gene transcripts:** CCNA1; KHDC1L; MBD3L2; PRAMEF6; SLC34A2; ZSCAN4

##### **Step 1 (Pre-Treatment data only): (By gene transcript)**

- I. Calculate Median (measure of average) of delta CT
  - a. **Rationale:** median is a robust measure of average, less sensitive to extreme values
- II. Calculate Median absolute deviation of delta CT (MAD: measure of variability)
  - a. **Rationale:** MAD is a robust measure of variability

##### **Step 2 (Pre-treatment and post-treatment: By gene transcript; by subject)**

- I. Use MAD obtained in Step 1 to calculate standardized score per gene transcript, per patient:

$$\text{Standardized Score} = (\text{Normalized Delta Ct Value} - \text{Median}) \div \text{MAD}$$

- a. **Rationale:** Standardize all gene measures to the same scale; reduce the impact of highly variable genes in the final composite measure
- II. Select median of standardized scores for each patient, across all genes, by visit.
  - a. Each patient's final score is the median standardized score across multiple transcripts.
  - b. This "composite score" is then used in the analysis for change from baseline.
  - c. Steps 1 and 2 may help resolve issue with censored (undetectable) data.

##### **NOTE:**

1. A composite score based on a simple average, across all 6 genes, per subject, per timepoint, may also be explored, to assess if a simpler approach to creating a composite score leads to equivalent interpretations of study results.
2. We will also explore composite scores based on the 6 genes: CCNA1; KHDC1L; PRAMEF6; SLC34A2; ZSCAN4; MBD3L2. The top two DUX4-driven transcripts will be identified as follow:
  - a. At baseline, select the two highest magnitude transcripts per subject.
  - b. For each subject, select only observations pertaining to only these two transcripts at both baseline and post-baseline. The two selected transcripts may vary across subjects.
  - c. Calculate the composite score (DUX4 score) using only these two transcripts, per subject, per timepoint.

Composite DUX4 score = arithmetic mean (transcript 1, transcript 2)

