#### 3.4.1 Assessment of DUX4 Activity

A subset of DUX4-gene transcripts will be measured in skeletal muscle biopsies, using validated QRT-PCR assays, to measure the treatment effect of losmapimod on aberrant DUX4 activity. A composite DUX4 score will be derived for each patient, at each time point based on normalized gene expression values for the panel of pre-selected genes.

The quantification of gene expression using qPCR, normalization of qPCR and derivation of the composite DUX4 score are conducted at a central laboratory (Q2 Lab Solutions). For details on assay validation, gene subset selection criteria/process, and derivation of the composite DUX4 Score, see Appendices 1 – 5.

All subjects will undergo up to two muscle biopsies; one at baseline, pre-treatment (Visit 4, Week 8 ± 1 week), the second on-treatment muscle biopsy approximately 4 or 8 weeks later (Visit 5, Week 14 ± 2 weeks). Up to 8 subjects will have the second on-treatment biopsy at 4 weeks (Biopsy Cohort Week 4) and up to 8 subjects will have the second on-treatment biopsy at 8 weeks (Biopsy Cohort Week 8).

The DUX4 composite score will be summarized as change from pre-treatment (Week 8 biopsy) to on treatment (Week 14 ± 2 weeks). If the pre-treatment or on-treatment DUX-4 results are unavailable, then the assessment is considered missing. Missing results will be imputed by mean, worst case, and median methods ([Section 2.3.6](#)).

The individual components of the composite DUX4 score will also be summarized at each timepoint, along with change from baseline for post-treatment visits.

An additional DUX4 composite score based on a simple average, across all 6 genes, per subject, per timepoint, will be summarized as change from pre-treatment (Week 8 biopsy) to on treatment (Week 14 ± 2 weeks), to assess if a simpler approach to creating a composite score leads to equivalent interpretations of study results.

Similarly, another additional DUX4 composite score based on a simple average, across the top 2 genes, per subject, per timepoint, will be summarized as change from pre-treatment (Week 8 biopsy) to on treatment (Week 14 ± 2 weeks).

Composite scores based on simple averages will not be imputed. Summaries presented for Biopsy Cohort Week 4, Biopsy Cohort Week 8, and overall.

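### The exploratory top-two DUX4 score picks each subject's transcripts on the same biopsy that serves as baseline, so its change is open to regression to the mean: a spurious fall if magnitude means highest expression

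*SAP*

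**What the plan says.** SAP 3.4.1 plans several summaries of DUX4 activity from muscle biopsies. The main one is a composite: the median of standardised scores over six transcripts. The individual transcripts, a simple average over all six, and a simple average over two are also summarised. The last is the subject of this point. It is averaged "across the top 2 genes, per subject, per timepoint, will be summarized as change from pre-treatment" to on-treatment.

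SAP Appendix 4, Note 2 gives the selection rule. It opens with "The top two DUX4-driven transcripts will be identified as follow", and step a reads "At baseline, select the two highest magnitude transcripts per subject". Step b keeps the chosen pair at baseline and post-baseline and adds: "The two selected transcripts may vary across subjects". The score is the arithmetic mean of the two.

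Protocol 8.2 and SAP 3.4.1 provide one pre-treatment biopsy (Visit 4) and one on-treatment biopsy (Visit 5). Protocol 10.1 confirms that every subject takes active drug from Visit 4. By contrast, the six-transcript panel was fixed beforehand: "Six DUX4-regulated gene transcripts were selected, a priori, to be in a composite DUX4 score" (SAP Appendix 1, step 3a).

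**The concern.** One measurement does two jobs: it decides which transcripts count, and it is the starting point from which their change is measured. A transcript can reach the top two because its true level is high or because error at that biopsy pushed it up. The true level persists to the second biopsy; the error, on average, does not. The selected baseline values are therefore too high on average, and the change is negative on average even if the drug does nothing.

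That is the direction the sponsor expects. Protocol 13.1 anticipates a DUX4 decrease of 50% or more. With no control arm, this score cannot show by itself how much of a fall comes from selection. A larger fall in the top two genes than in all six could be read as a stronger drug effect where DUX4 is most active, when selection alone would produce that pattern.

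**Working it through.** The documents state no expected change, standard deviation or power for this score, so there is no figure to reproduce. The check asks what the rule gives when the drug has no effect.

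**Inputs from the documents.** Six candidate transcripts, two selected per subject, score = mean of the two (SAP Appendix 4); one pre-treatment biopsy (Protocol 8.2, SAP 3.4.1).

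**Assumptions.** Highest expression is ranked; errors are normal; 1 Ct is a two-fold difference. Let sw be the transcript-specific SD from biopsy to biopsy, in Ct on an expression scale (higher = more expression). Error shared by all transcripts in a biopsy does not alter the ranking and adds no bias.

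**Case A: transcript levels vary at random within a subject, with SD sb and a common mean.** The expected largest and second largest of six standard normal values are 1.2672 and 0.6418, with mean (1.2672 + 0.6418)/2 = 0.9545. The selected pair therefore sits 0.9545 × √(sw² + sb²) above the subject's average at baseline. A share sw²/(sw² + sb²) of that excess is error and is lost at the second biopsy:

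expected change = -0.9545 × sw² / √(sw² + sb²).

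For sw = 0.5, sb = 1: 0.25/√1.25 = 0.2236; × 0.9545 = 0.213 Ct; 2^(-0.213) = 0.86, an apparent fall of 14%.
For sw = 1, sb = 0.5: 1/√1.25 = 0.894; × 0.9545 = 0.854 Ct; 2^(-0.854) = 0.55, a fall of 45%.

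| sw | sb 0.5 | sb 1 | sb 2 | sb 3 |
|---|---|---|---|---|
| 0.3 | -10% | -6% | -3% | -2% |
| 0.5 | -21% | -14% | -8% | -5% |
| 1 | -45% | -37% | -26% | -19% |

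Simulation with 300,000 subjects per cell agrees with the formula to within 0.005 Ct.

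**Case B: the six levels are the same in every subject and equally spaced** (simulated, same size).

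| sw | 0.5 Ct apart | 1 Ct | 2 Ct | 3 Ct |
|---|---|---|---|---|
| 0.3 | -3% | 0% | 0% | 0% |
| 0.5 | -11% | -4% | 0% | 0% |
| 1 | -37% | -21% | -7% | -2% |

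When levels are far apart, nearly the same pair is chosen whatever the error, and the bias disappears.

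**Other readings of magnitude.** Ranking on lowest expression under Case A mirrors the result: +0.029 Ct (+2%) at sw 0.3, sb 3, and +0.854 Ct (+81%) at sw 1, sb 0.5. Ranking on absolute value, symmetric about zero, gives a mean change within 0.004 Ct of zero. That cancellation needs symmetry, which a detection floor would break, and SAP Appendix 4, Step 2 acknowledges undetectable values: "Steps 1 and 2 may help resolve issue with censored (undetectable) data".

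**Effect on a real change.** With a true change of -1 Ct (-50%), sw 0.5 and sb 1, the score reads -1 - 0.213 = -1.213 Ct; 2^(-1.213) = 0.43, so -57%.

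**Comparator.** In a separate simulation with no drug effect and trials of 14 subjects, the mean of all six transcripts changed by between -0.006 and +0.005 log2 units in every scenario. The bias does not shrink with sample size.

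**The case against.** The strongest objection is that the direction rests on a word the visible text does not define. Appendices 2, 3 and 5 are not in the available text and may define it. Two clues point to highest expression. Note 2 describes the chosen transcripts as the leading DUX4-driven ones. The worst-case imputation rule in SAP 2.3.6 takes the minimum for a missing pre-treatment value and the maximum for a missing post-treatment value, so a higher composite score is treated as worse. Neither clue is decisive. The imputation rule concerns the main composite, and SAP 3.4.1 says simple-average scores are not imputed. This objection stands, so the direction can only be stated conditionally.

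The size is also not anchored in the documents, and Case A, with one common mean level, favours the bias. That stands too; Case B shows that the bias can be nil.

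Three stronger readings are tempting and are not supported:

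- A reader might infer that wide separation between transcript levels gives no protection, because Step 2 aims to "Standardize all gene measures to the same scale". That would hold if standardised scores were ranked, but SAP 3.4.1 describes the top-two score as a simple average, and nothing visible says that standardised values feed it.
- A reader might infer that the study has no means of telling selection from drug effect. The score alone has none, but SAP 3.4.1 already plans the unselected six-gene scores and the individual transcripts, which are an internal check.
- A reader might treat the absence of DUX4 from the list in SAP 3.6 ("Sensitivity analyses will be conducted using an alternative baseline defined as the mean of all available pre-treatment measures") as an oversight. With one pre-treatment biopsy there is nothing to average. The omission only means that this analysis offers no remedy here.

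**Conclusion.** The point holds in conditional form and is minor. Selection and baseline share one biopsy. If magnitude means highest expression, any transcript-specific biopsy-to-biopsy error that can affect the ranking produces an expected fall with no drug effect. Under the assumed SDs the fall runs from about 0 to about 45%. A low-expression ranking would give a spurious rise instead, and a symmetric absolute ranking roughly no mean shift.

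The reach is narrow. The top-two score is an additional exploratory summary. Protocol 8.1.1 does not name it as an endpoint, SAP 4.1 does not list it for the first interim analysis, and it has no decision rule; SAP 2.4 rules out formal tests. The selection rule does not touch the six-gene median, the six-gene average, the individual transcripts or the safety endpoint.

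**What to change.** In SAP Appendix 4, Note 2a and SAP 3.4.1:

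1. State the scale and sign on which magnitude is ranked, or cite the appendix that gives them.
2. Label the top-two change as subject to regression to the mean, because selection and baseline use the same biopsy.
3. Present it only beside the six-gene median, the six-gene average and the individual transcripts.
4. Draw no conclusion about DUX4 reduction from it unless those agree.

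This costs wording only and needs no new data or analysis. The price is that the score carries less weight.

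Optionally, add a score that uses one fixed pair for all subjects, provided a documented and dated ranking from outside this trial's baseline data exists. The data behind the a priori choice of the six transcripts are a possible source, but the visible text does not show that they yield a ranking. A fixed pair removes this bias but has costs. It is a different quantity from the subject-specific score, it may be undetectable in some subjects, and it would be named after data collection in an open-label study. It should therefore be an addition, not the main remedy.
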